7.2.2.5. Feminine Product Return Rate at Week 52/EOT

To quantify degree of compliance with feminine product collection, the FPRR will be calculated based on the inventory of feminine product returned by day (dates) summarized on the Feminine Product Collection eCFR page (provided by the vendor, KCAS) and responses to the paper patient Diary questions regarding bleeding experience and the use of feminine product obtained for the corresponding Diary window (see [Table 7](#)). Specifically:

- For those who returned feminine product at Week 52/EOT, the FPRR was calculated as the observed number of days with returned feminine products (based on the inventory of FP received by KCAS) divided by the expected number of days with bleeding and use of product as reported on the patient's paper Diary within the Week 52/EOT feminine product collection interval (as defined above).
- For those who did not return any feminine products:
 - If the reason was amenorrhea reported on the eCRF or if spotting/negligible bleeding was reported on the eCRF and confirmed by patient's paper Diary over the Week 52/EOT visit window, their FPRR will be set to 100% because the lack of menstruation obviates the need for feminine product collection.
 - Otherwise if the reason is any other, their FPRR was set to 0.

$$\text{FPRR} = \frac{\text{observed (No. of days with returned FP [per KCAS])}}{\text{expected (No. of days reported bleeding and use of FP [per Diary])}} \times 100$$

7.2.3. Definition of Responder Status at Week 52/EOT

A responder at Week 52/EOT is defined as a patient who satisfies both the following:

- Had MBL volume of < 80 mL at Week 52/EOT;
- Had at least a 50% reduction from Baseline in MBL volume at Week 52/EOT.

The reduction from Baseline in MBL volume at Week 52/EOT will be calculated as the absolute change at Week 52/EOT in MBL volume from the Baseline MBL volume divided by the Baseline MBL volume.

Responder status at Week 52/EOT will be assessed based on the reported MBL volume at Week 52/EOT, in conjunction with treatment duration, compliance with feminine product collection, and compliance with paper patient Diary entry over the same visit window (see [Section 7.2.4](#) for details).

- For patients who did not return a feminine product collection, responder status will be determined depending on the reason reported on the Feminine Product Collection eCRF:
 - If the reason is reported as Amenorrhea, the last 35 days of treatment will be used to derive responder status:
 - If the Week 52/EOT interval was 35 days, then she will be considered as a responder;

- If the Week 52/EOT interval was <35 days, the following supportive information will be used to derive responder status:
 - If a patient reported amenorrhea at the visit prior to Week 52/EOT, she will be defined as a responder;
 - If a patient did not report amenorrhea at the visit prior to Week 52/EOT, paper Diary data from the prior visit interval will be reviewed to confirm whether the patient was amenorrheic for a total of 35 days.
 - If the paper Diary from the previous interval confirms amenorrhea, then the patient will be considered as a responder;
 - Otherwise, **MBL volume will be considered missing and LOCF observed MBL volume will be used to determine responder status.**
- If the reason is Other and the specification describes spotting or negligible bleeding, responder status will be defined as follows:
 - The patient will be considered as a responder if it is supported by the paper Diary data: the paper Diary entry rate must exceed 70% and the patient must have reported no more than 5 total days of bleeding with product use and no more than 3 consecutive bleeding with product use over the collection interval.
 - If the paper Diary entries did not confirm spotting or negligible bleeding, **MBL volume will be considered missing and LOCF observed MBL volume will be used to determine responder status.**
- If the reason is any Other, the responder status will be derived as follows:
 - **MBL volume will be considered missing. LOCF observed MBL volume will be used to determine responder status.**
- Patients with no visit within the FP collection interval for Week 52/EOT. **MBL volume will be considered missing and LOCF observed MBL volume will be used to determine responder status.**

Table 9: LOCF Approach for Derivation of Responder Status at Week 52/EOT and Missing Data Handling Rules – for Primary Analysis

Study Disposition	FP Collection (FPRR)	Observed MBL Volume	Reason for No FP Collection	Responder Status
Discontinued early due to lack of	N/A	N/A	N/A	Non-responder

efficacy or for surgical intervention for uterine fibroids				
Completed study or discontinued early for other reasons	100% FP Compliance	N/A	N/A	Responder based on the observed MBL volume
	<100% FP Compliance	MBL volume \geq 80 mL or <50% reduction from Baseline	N/A	Non-responder based on the observed MBL volume
		MBL volume < 80 mL and \geq 50% reduction from Baseline	N/A	Based on LOCF MBL volume
	No FP Collection	N/A	Reported “Amenorrhea” ^a	Responder
			Reported “Spotting or negligible bleeding” confirmed by Diary ^b	Responder
			Reported “Amenorrhea” or “Spotting or negligible bleeding” which was not confirmed, or other reason for no FP collection	Based on LOCF MBL volume

Abbreviations: FP, feminine product; EOT, end of treatment; MBL, menstrual blood loss; N/A, not available.

^a Amenorrhea confirmed if Week 52/EOT visit interval is \geq 35 days, if amenorrhea reported at prior visit, or if paper diary confirms no bleeding/spotting with use of feminine product for a total of 35 days.

^b Defined as those patients who meet the following criteria: Diary entry rate > 70% and no more than 3 consecutive days and no more than 5 total days of bleeding/spotting and use of feminine product reported on the Diary over the Week 52/EOT visit window (see [Table 7](#)).

7.2.5. Subgroup Analyses

Subgroup analyses of the primary efficacy endpoint will be performed to assess whether response rate is consistent across clinically important subgroups. The response rate and 95% CI may be displayed in a separate forest plot for each subgroup. Subgroups will include, but will not be limited to, the subgroups outlined in [Table 10](#).

Table 10: Planned Subgroup Analyses

Subgroup Name	Subgroup Level
Geographic region	North America vs Rest of World

Menstrual blood loss volume at Baseline (mL)	< 225 vs \geq 225 < 120, 120 to < 160, 160 to < 225, \geq 225
Age category (years)	< 40 vs \geq 40 < 35, 35 to < 40, 40 to < 45, \geq 45
Race	Black or African American vs Not Black or African American; Black or African American, White, Other
Volume of myoma at Baseline (cm ³)	< 25 vs \geq 25
Volume of uterus at Baseline (cm ³)	< 300 vs \geq 300
BMI (kg/m ²) at Baseline	< 30 vs \geq 30 < 25, 25 to < 30, 30 to < 35, 35 to < 40, \geq 40
Maximum NRS score for uterine fibroid-associated pain at Baseline	< 4 vs \geq 4
History of prior pregnancy	Yes/No
Alcohol Use	None, Moderate, Heavy
Smoking History	Never Smoker, Former Smoker, Current Smoker

Abbreviations: BMI = body mass index; NRS = Numerical Rating Scale.

7.3. Secondary Efficacy Endpoints

All efficacy and safety measures over the course of both the parent and extension studies will be presented by the parent study treatment group using descriptive statistics. No treatment comparisons will be performed for this extension study.

7.3.1. Percent Change from Baseline to Week 52 in MBL Volume

The percent change in MBL volume from baseline will be summarized descriptively at each visit. The LS means and 95% CI will be derived using a mixed-effects model with repeated measures and presented as describe in [Section 7.1.2](#). Observed MBL volume for each timepoint will be used, regardless of FPRR. No imputations will be made for missing values.

7.3.2. Proportion of Women Who Achieve Amenorrhea Over the Last 35 Days of Treatment

7.3.2.1. Determination of Amenorrhea

Rules for determining amenorrhea in the treatment period is defined as those who meet 1 of the following requirements for 2 consecutive visits (approximately 56 consecutive days). Patients will be deemed to have amenorrhea during a visit window according to the following rules:

- No feminine product returned due to reported amenorrhea in 2 consecutive visits

OR

- No feminine product returned due to other reasons or feminine product collection with a negligible observed MBL volume coupled with other data indicating infrequent non-cyclic bleeding/spotting as described in [Table 11](#).

Missing responses for menstrual bleeding questions in the paper Diary will be treated as “No Bleeding” if paper Diary compliance rate is > 70%.

Table 11: Rules for Determining Amenorrhea by Visit

Feminine Product Collection (KCAS) ^a	Patient’s Paper Diary
No feminine product collection due to reported amenorrhea	N/A
No feminine product collection due to other reasons	
 • Data indicating infrequent, non-cyclic bleeding/spotting defined as bleeding/spotting with feminine product use for no more than 3 consecutive days and no more than 5 days bleeding total per visit window • Diary entry rate > 70%
Feminine product collection with negligible observed MBL volume defined as <5 mL	
 • Data indicating infrequent, non-cyclic bleeding/spotting defined as bleeding/spotting with feminine product use for no more than 3 consecutive days and no more than 5 days bleeding total per visit window • Diary entry rate > 70%

Abbreviations: eCRF, electronic case report form; MBL, menstrual blood loss; N/A = not applicable.

^a There is no requirement for feminine product return rate, as the determination of amenorrhea is based on the Diary response.

Patients with amenorrhea over the last 35 days of treatment are defined as those who meet the definition of amenorrhea. If a patient does not return for her Week 52/EOT visit, the paper Diary responses for the last 35 days of treatment will be evaluated, if available. If the criteria for infrequent, non-cyclic bleeding or spotting as indicated in [Table 11](#) is met and the criteria for amenorrhea is met at the prior visit, the patient will be categorized as amenorrheic at Week 52/EOT.

Patients missing amenorrhea reporting for all visits in the extension study will carry forward their Week 24/EOT amenorrhea status from the parent study as their Week 52/EOT amenorrhea status.

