	
Primary Efficacy Endpoint
 
 Proportion of women who achieve or maintain a menstrual blood loss volume of < 80 mL AND at least a 50% reduction from parent study Baseline to the last 35 days of treatment, as measured by the alkaline hematin method. 
Secondary Efficacy Endpoints
 
 Time to achieve a menstrual blood loss volume of < 80 mL AND at least a 50% reduction from parent study Baseline menstrual blood loss volume as measured by the alkaline hematin method; Change from parent study Baseline to Week 52 in menstrual blood loss; Proportion of women who achieve or maintain amenorrhea over the last 35 days of treatment; Proportion of women with a hemoglobin below the lower limit of normal at parent study Baseline who achieve an increase of ≥ 1 g/dL from parent study Baseline at Week 52; Proportion of women with a hemoglobin below the lower limit of normal at parent study Baseline who achieve a normal hemoglobin at Week 52; Change from parent study Baseline to Week 52 in hemoglobin; Change from parent study Baseline to Week 52 in the Uterine Fibroid Scale – Symptom Severity; Change from parent study Baseline to Week 52 in the Uterine Fibroid Scale – Health-related Quality of Life subscales and total score; Change from parent study Baseline to Week 52 in the MIQ score for physical activities; Change from parent study Baseline to Week 52 in the MIQ score for social and leisure activities; Change from parent study Baseline to Week 52 in uterine volume; Change from parent study Baseline to Week 52 in uterine fibroid volume. 
Safety Endpoints
 
 Incidence of adverse events; Percent change from the parent study Baseline to Week 52 in bone mineral density at the lumbar spine (L1-L4), femoral neck, and total hip as assessed by DXA. 
Pharmacodynamic Endpoint
 
 Change from parent study Baseline to Week 52 in pre-dose concentrations of serum estradiol. 
Exploratory Endpoint
 
 Change from parent study Baseline to Week 52 in the EQ-5D-5L.

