7.2.2. Definitions Related to Menstrual Blood Loss

The data sources that will be used to support derivation of responder status include:

- Menstrual blood loss volume determined by the alkaline hematin method;
- Daily patient report of bleeding (yes/no) and use of feminine product (yes/no) captured in the paper patient Diary;
- The status of feminine product (FP) collection return (yes/no) recorded on the electronic case report form (eCRF) page at each visit with specific reasons captured when no product collection was returned.

The total MBL volume is reported from the analysis of FP returned for each collection interval. An inventory of days (with dates) for which FP was collected and returned is also available. This inventory is aligned with patients' reports of bleeding and FP use in the paper patient Diary. The status of FP collection return, and specifically the reason for non-return of FP reported on the Feminine Product Collection eCFR page is used to support derivation of responder status (see [Section 7.2.4](#) for details).

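### SAP 7.3.2.1 scores amenorrhea over two consecutive visits (about 56 days) but reports it as amenorrhea over the last 35 days

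*SAP*

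**What the plan says.** The protocol synopsis lists the secondary endpoint "Proportion of women who achieve or maintain amenorrhea over the last 35 days of treatment". Protocol Sections 3 and 9.4 and SAP Table 1 repeat it, and the SAP 7.3.2 heading reads "Proportion of Women Who Achieve Amenorrhea Over the Last 35 Days of Treatment".

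The derivation in SAP 7.3.2.1 begins: "Rules for determining amenorrhea in the treatment period is defined as those who meet 1 of the following requirements for 2 consecutive visits", and gives the span as roughly 56 days in a row. Table 11 lists three ways in which a visit window can qualify:

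- no product returned because amenorrhea was reported;
- no product returned for another reason, with a diary showing at most 3 consecutive and 5 total bleeding days with product use, and an entry rate above 70%;
- product returned but under 5 mL, with the same diary conditions.

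One sentence ties this rule to the label: "Patients with amenorrhea over the last 35 days of treatment are defined as those who meet the definition of amenorrhea". A 35-day reading of the diary appears in this section only for a missed final visit: "If a patient does not return for her Week 52/EOT visit, the paper Diary responses for the last 35 days of treatment will be evaluated". Even then she must also meet the criteria at the prior visit. On gaps in the diary, the section says: "Missing responses for menstrual bleeding questions in the paper Diary will be treated as" no bleeding, provided that diary compliance is above 70%.

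SAP 7.2.4, written for the primary endpoint, handles the same concept over 35 days. If the final collection interval is shorter than that and amenorrhea was not reported at the preceding visit, "paper Diary data from the prior visit interval will be reviewed to confirm whether the patient was amenorrheic for a total of 35 days".

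**The concern.** The rule and its label cover different periods. A woman who stopped bleeding before the last 35 days, but after the start of the two-visit span, meets the stated endpoint and fails the derivation. The SAP would then call her amenorrheic for 35 days under one section and not amenorrheic over the last 35 days under another.

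No comparison between groups is planned, so the absolute proportion in each parent-study group is the whole result for this endpoint. A reader who takes the 35-day label at face value will misread what was counted. In addition, wherever status depends on the diary, it can rest on days for which nothing was recorded, and the plan has no analysis that shows how much this matters.

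**Working it through.** **1. The plan's own figure.** SAP Table 2 target days are Week 44 = 309, Week 48 = 337 and Week 52 = 365. Two visit intervals span 365 − 309 = 56 days, which reproduces the SAP's figure.

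**2. Scored period against stated period, at target days.**
- Scored: days 310 to 365, that is 365 − 310 + 1 = 56 days.
- Stated: days 331 to 365, that is 365 − 331 + 1 = 35 days.
- Scored but not stated: days 310 to 330, that is 56 − 35 = 21 days, or 21/56 = 37.5% of the scored period.
- Of the 35 stated days, 7 (331 to 337) lie in the Week 48 interval and 28 (338 to 365) in the Week 52 interval. Data from both intervals are needed, but not all of the earlier one.

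**3. Visit tolerances.** Protocol Table 1 allows ±7 days at Week 44 and ±10 at Week 52. The span runs from 56 − 17 = 39 to 56 + 17 = 73 days. For women seen on schedule it exceeds 35 days by 4 to 38 days, so the tolerances do not remove the mismatch.

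**4. One woman under both sections.** She bleeds on days 312 to 317, returns 30 mL at Week 48, has no further bleeding and reports amenorrhea at Week 52. She has 365 − 317 = 48 bleed-free days.
- *SAP 7.2.4:* her Week 52 interval is 28 days and she did not report amenorrhea at Week 48, so the prior interval's diary is checked. Days 331 to 337 are clear, and she is confirmed over 35 days.
- *SAP 7.3.2.1:* her Week 48 window fails every row of Table 11. Product was returned, so the two non-return rows do not apply, and 30 mL is not under 5 mL. She is scored not amenorrheic.

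**5. Blank diary days.** In a 28-day window the entry rate must exceed 0.70 × 28 = 19.6, so 20 entries (71.4%) suffice and 8 days may be blank. In a 35-day window it must exceed 24.5, so 25 entries suffice and 10 may be blank. Either number of blanks is above the 5-day limit, so a woman with no recorded bleeding can owe her status to the blank-day rule.

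**6. Effect on the rate.** The documents give no amenorrhea rates. As an illustration only, assume that 60% are amenorrheic over the last 35 days and that a fraction f of them bled earlier in the two-visit span in a way that fails Table 11. The scored rate is 60% × (1 − f): 57%, 54%, 48% or 42% for f = 5%, 10%, 20% or 30%. Both inputs are assumptions.

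**The case against.** Visits are 28 days apart, so one interval cannot cover 35 days at target days, and two is the smallest whole number that does. The two-visit span then contains the last 35 days, so the rule errs on the strict side. The length is disclosed in the same sentence as the rule. SAP Section 1 says that methods are consistent with the parent studies. The endpoint is descriptive and untested.

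Most of this stands, and it limits the point to a mismatch of definition and label. It does not justify the mismatch: needing data from two intervals is not the same as needing both to be clear, and SAP 7.2.4 already reaches 35 days without that demand. The containment argument also sets aside the spotting tolerance, which is counted per visit window. Three spotting days in days 331 to 337 and four separate ones in days 338 to 365 can pass both windows, yet total 7 in the stated 35 days.

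Three stronger readings are tempting but not supported:

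- *That the second bullet of 7.3.2.1 needs only one visit, leaving 7 of the 35 days unexamined.* The lead-in most naturally governs both bullets. A 28-day window also holds only at target days, because SAP Table 7 starts the final window after the previous visit with returned product.
- *That blank days should count against the woman in the main estimate.* With no recorded bleeding, at most 5 blanks would then be allowed, which over 35 days means 30/35 = 85.7% entry. That would replace the 70% limit with a worst-case assumption. It belongs in a sensitivity analysis.
- *That the reported rate is biased in a known direction.* For women bleed-free over the last 35 days the longer window can only remove, while reading blanks as no bleeding can only add. The net effect is unknown.

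**Conclusion.** The mismatch is real. The proportion reported under a 35-day label is derived over about 56 days, and 21 of those days precede the stated window at target days. The window is stricter than the label, and a woman with 48 bleed-free days can be excluded. The day counts rest on the SAP Table 2 target days; with the protocol's tolerances the excess is 4 to 38 days for women seen on schedule. No shift in the rate can be given.

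Severity is modest. This is a secondary endpoint with no test, sample size or comparison attached, and the primary responder rate has its own rules in SAP 7.2.4. Whether the two-visit rule matches the parent studies cannot be checked, because their SAP is not among the documents.

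**What to change.** In SAP 7.3.2.1:

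1. Derive the endpoint on the last 35 days from the diary, the collection eCRF and the dated product inventory, drawing on the prior interval to reach 35 days as 7.2.4 does. Apply the 3-consecutive and 5-total diary limits to those 35 days. Keep the under-5 mL route, but test the volume of each whole collection interval that holds product dated inside the 35 days, because "The total MBL volume is reported from the analysis of FP returned for each collection interval" and one total cannot be split by day.
2. Report the existing two-visit rule beside it for comparability with the parent studies, labelled as amenorrhea or infrequent spotting over two consecutive visits (about 56 days).
3. Keep the blank-day rule (no bleeding when entry exceeds 70%) in the main estimate. Add a sensitivity estimate in which a woman counts as not amenorrheic when her blanks could breach the 3-consecutive or 5-total limit. It should cover every route that relies on the diary: other-reason non-returns, the under-5 mL route, the missed final visit, and the prior-interval days that step 1 newly uses.

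The cost is one added derivation and one sensitivity estimate from data already collected. The 35-day figure may not match the parent-study definition, which is why both are shown. The whole-interval volume test is slightly strict, since it can include blood lost before the 35 days.

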7.3.3. Change from Baseline in Hemoglobin

The change in hemoglobin throughout the extension study is evaluated in two subsets of patients. Women with hemoglobin < 11.6 g/dL at baseline meet the definition for below the lower limit of normal. Women with hemoglobin ≤ 10.5 g/dL at baseline meet the criteria for anemia.

The change from baseline and percent change from baseline in hemoglobin will be summarized for each scheduled visit as described in [Section 7.1.2](#). The analysis will be restricted to women with values ≤ 10.5 g/dL at baseline.

The proportion of with an increase in hemoglobin of > 2 g/dL will be summarized for women with hemoglobin values ≤ 10.5 g/dL at baseline. The proportion of with an increase in hemoglobin of ≥ 1 g/dL at Week 52 will be summarized for women with hemoglobin values < 11.6 g/dL at baseline.

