
 • To evaluate long-term efficacy of relugolix 40 mg once daily co-administered with low-dose estradiol and norethindrone acetate for up to 52 weeks, among patients who previously completed a 24-week treatment period in one of the parent studies (MVT-601-3001 or MVT-601-3002), on the following: 
 ○ Achievement/maintenance of amenorrhea; ○ Hemoglobin; ○ Changes in symptom severity and quality of life related to uterine fibroids as measured by the Uterine Fibroid 	
 • Time to achieve a menstrual blood loss volume of < 80 mL AND at least a 50% reduction from parent study Baseline menstrual blood loss volume as measured by the alkaline hematin method; • Change from parent study Baseline to Week 52 in menstrual blood loss; • Proportion of women who achieve or maintain amenorrhea over the last 35 days of treatment; • Proportion of women with a hemoglobin below the lower limit of normal at parent study Baseline who achieve an increase of

Objective(s)	Endpoint(s)

Symptom and Health-Related Quality of Life (UFS-QoL);
 
 ○ Impact of heavy menstrual bleeding on social, leisure, and physical activities as measured by the Menorrhagia Impact Questionnaire (MIQ); ○ Uterine volume; ○ Uterine fibroid volume. 	
≥ 1 g/dL from parent study Baseline at Week 52;
 
 ● Proportion of women with a hemoglobin below the lower limit of normal at parent study Baseline who achieve a normal hemoglobin at Week 52; ● Change from parent study Baseline to Week 52 in hemoglobin; ● Change from parent study Baseline to Week 52 in the Uterine Fibroid Scale – Symptom Severity; ● Change from parent study Baseline to Week 52 in the Uterine Fibroid Scale – Health-related Quality of Life subscales and total score; ● Change from parent study Baseline to Week 52 in the MIQ score for physical activities; ● Change from parent study Baseline to Week 52 in the MIQ score for social and leisure activities; ● Change from parent study Baseline to Week 52 in uterine volume; ● Change from parent study Baseline to Week 52 in uterine fibroid volume.
Safety	

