Baseline menstrual blood loss is defined as the average menstrual blood loss from the two Screening menstrual cycles used to meet the inclusion criteria prior to the date of the first dose of study drug in the parent study as assessed by the alkaline hematin method. The menstrual blood loss during the last on-treatment cycle (Week 52) is the total menstrual blood loss during the last 35 days on treatment as assessed by the alkaline hematin method.

Patients from Group C, who discontinue the extension study before Week 32 (28 days) will be considered non-responders.

For the endpoints of time to achieving a menstrual blood loss volume of < 80 mL AND at least a 50% reduction from parent study Baseline menstrual blood loss volume, time to event will be defined as weeks from randomization in the parent study to first occurrence of the event as assessed by the alkaline hematin method. Patients without an event will be censored at last assessment date prior to the end of study. Kaplan-Meier methods will be used to describe the time to event distributions for each parent study treatment arm.

Descriptive statistics will be provided for changes in menstrual blood loss, hemoglobin, Uterine Fibroid Scale – Symptom Severity, Menorrhagia Impact Questionnaire Score, Numerical Rating

Scale score for uterine fibroid-associated pain, uterine volume, and uterine fibroid volume to parent study Baseline.

For binary endpoints, the point estimate and 2-sided 95% CI for the proportion will be provided by parent study treatment group.

Details on the endpoint analyses including derivations, handling of missing data, and statistical methods will be provided in the SAP.

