
 • To evaluate long-term efficacy of relugolix 40 mg once daily co-administered with low-dose estradiol and norethindrone acetate for up to 52 weeks, among patients who previously completed a 24-week treatment period in one of the parent studies (MVT-601-3001 or MVT-601-3002), on the following: 
 ○ Achievement/maintenance of amenorrhea; ○ Hemoglobin; ○ Changes in symptom severity and quality of life related to uterine fibroids as measured by the Uterine Fibroid Symptom and Health-Related Quality of Life (UFS-QoL); ○ Uterine volume; ○ Uterine fibroid volume. 	
 • Change from parent study Baseline to Week 52 in menstrual blood loss (MBL); • Proportion of women who achieve or maintain amenorrhea over the last 35 days of treatment; • Proportion of women with a hemoglobin below the lower limit of normal at parent study Baseline who achieve an increase of ≥ 1 g/dL from parent study Baseline at Week 52; • Proportion of women with a hemoglobin ≤ 10.5 g/dL at parent study Baseline who achieve an increase of > 2 g/dL from parent study Baseline at Week 52; • Change from parent study Baseline to Week 52 in hemoglobin; • Change from parent study Baseline to Week 52 in the Uterine Fibroid Scale – Symptom Severity; • Change from parent study Baseline to Week 52 in the Uterine Fibroid Scale – Health-related Quality of Life subscales and total score; • Change from parent study Baseline to Week 52 in the UFS-QoL Bleeding and Pelvic Discomfort Scale score, a sub-

Objective(s)	Endpoint(s)
	
scale of the UFS-QoL Symptom Severity scale
 
 • Change from parent study Baseline to Week 52 in uterine volume; • Change from parent study Baseline to Week 52 in uterine fibroid volume.
Safety	

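### The SAP drops the group summaries of four of the protocol's 12 secondary endpoints without a stated reason and, separately, limits hemoglobin change to women at or below 10.5 g/dL at baseline

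*SAP*

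**What the plan says.** The protocol gives the same 12 secondary efficacy endpoints in the Synopsis, Section 3 and Section 9.4. Four of them matter most here, besides change in hemoglobin, which carries no restriction on its baseline value. The first is a time-to-event endpoint for MBL response, worded as "Time to achieve a menstrual blood loss volume of < 80 mL AND at least a 50% reduction from parent study Baseline". The second concerns recovery from a low starting hemoglobin and requires a value in the normal range at Week 52. The third and fourth are MIQ change scores, one for limits on physical activity and one for limits on social and leisure life.

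Protocol 9.4 specifies Kaplan-Meier curves by parent study arm for the time-to-response endpoint and descriptive statistics for change in MIQ and hemoglobin. It adds: "Details on the endpoint analyses including derivations, handling of missing data, and statistical methods will be provided in the SAP".

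SAP Table 1 lists 10 secondary endpoints, including "Change from parent study Baseline to Week 52 in hemoglobin", again unrestricted. SAP 7.3 says that all efficacy measures will be described by parent study group. SAP 7.3.6 provides only a by-patient listing of MIQ. On hemoglobin, SAP 7.3.3 opens with "The change in hemoglobin throughout the extension study is evaluated in two subsets of patients". These are women below 11.6 g/dL (the lower limit of normal) and women at or below 10.5 g/dL. For change and percent change it then states: "The analysis will be restricted to women with values ≤ 10.5 g/dL at baseline".

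**The concern.** There are two separate problems.

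The first is omission. If the SAP is followed as written, two pre-specified endpoints have no result, and the protocol's MIQ objective has no summary. SAP 1.1 explains its added endpoints, partly by reference to emerging data, and SAP 4.2 explains the change of analysis population. Nothing explains the removals. In an open-label study, a reader of the SAP alone cannot tell whether they were decided independently of emerging results.

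The second is a contradiction. SAP 7.3.3 analyses hemoglobin change in a different population from the one that the protocol and the SAP's own Table 1 describe. The subset is defined by a low value of the same measurement from which change is calculated, so part of its mean rise needs no treatment effect.

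**Working it through.** **Endpoint count.** The protocol Synopsis set against SAP Table 1 and SAP 7.3:

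| Protocol secondary endpoint | In SAP Table 1? | Analysis in SAP |
|---|---|---|
| Time to MBL response | No | None |
| Change in MBL | Yes | 7.3.1 |
| Amenorrhea, last 35 days | Yes | 7.3.2 |
| Low baseline hemoglobin, rise ≥ 1 g/dL | Yes | 7.3.3 |
| Low baseline hemoglobin, normal at Week 52 | No | None |
| Change in hemoglobin | Yes | 7.3.3, baseline ≤ 10.5 g/dL only |
| UFS-QoL Symptom Severity | Yes | 7.3.4 |
| UFS-QoL quality-of-life scales and total | Yes | 7.3.4 |
| MIQ physical activities | No | 7.3.6, listing only |
| MIQ social and leisure activities | No | 7.3.6, listing only |
| Uterine volume | Yes | 7.3.5 |
| Fibroid volume | Yes | 7.3.5 |

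SAP Table 1 has 10 = 8 kept + 2 added (hemoglobin rise > 2 g/dL from ≤ 10.5 g/dL, and the Bleeding and Pelvic Discomfort Scale). Omitted: 12 − 8 = 4, of which 2 have no analysis and 2 are listed only. The protocol file contains two versions with the same 12 endpoints, so the count does not depend on which is used.

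**MIQ volume.** Protocol 6.2 sets on-treatment visits at Weeks 28, 32, 36, 40, 44, 48 and 52, which is 7 visits, and MIQ is completed at each (protocol 6.6.1.5). With about 600 women, 7 × 600 = about 4,200 questionnaires would be listed but not summarised. This is a maximum that assumes full attendance. The two omitted endpoints themselves use only the Week 52 questionnaires, at most about 600.

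**Hemoglobin coverage.** SAP 7.3.3 has four summaries, and its cut-points make three baseline bands:

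| Baseline (g/dL) | Change | Percent change | Rise > 2 | Rise ≥ 1 | Total |
|---|---|---|---|---|---|
| ≤ 10.5 | yes | yes | yes | yes | 4 |
| > 10.5 to < 11.6 | no | no | no | yes | 1 |
| ≥ 11.6 | no | no | no | no | 0 |

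The two responder columns are limited to low baselines by definition. The restriction that conflicts with the stated endpoint is the one on change, so 1 of the 8 kept endpoints is narrowed.

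**Direction of bias.** Under SAP 4.3.7, baseline is the last measurement before the first dose in the parent study. That one value both selects the woman and anchors her change. Women selected for a low reading are, on average, partly low by chance, and later readings drift back up. The 7.1.2 model is fitted separately in each group; adjusting for baseline within a group does not remove this drift. At Week 52 every group is on active drug, so none shows the drift alone. Group C's placebo visits up to Week 24, which the SAP 4.3.8 windows include, may show part of it. The documents give no hemoglobin mean, SD or within-woman correlation, so no size in g/dL can be calculated.

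**The case against.** The strongest objection is that protocol 9.4 promises only descriptive statistics for hemoglobin change, and SAP 9.2 presents change from Baseline at every visit, by parent study group, for each laboratory test. All-women results are therefore not lost. That stands. What is missing for all women is the LS mean and CI that SAP 7.1.2 sets for endpoints of change to Week 52. SAP 7.3.3 and SAP Table 1 still describe different endpoints. The laboratory shift tables do not replace the normal-hemoglobin endpoint either, because they use the worst post-Baseline result across both studies, not Week 52.

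The study is also purely descriptive, with no formal testing. That lowers the stakes, but in such a study the summaries are the result.

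The SAP states that its methods are consistent with the parent studies, and SAP 4.2 sends efficacy data up to 24 weeks to the Integrated Summary of Efficacy. Either might lie behind the removals; neither is given as the reason. The study report, prepared to ICH E3, may explain them later. The UFS-QoL activity scales are still summarised, but that is a different instrument with its own protocol endpoints.

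One practical point holds: MIQ items refer to the most recent menstrual period (protocol Appendix 1), and many women may have none by Week 52. An MIQ summary needs a stated rule for them.

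**Conclusion.** Both parts hold. Four of 12 protocol secondary endpoints lose their group summary without a reason in the available text: two have no analysis and two are listed only. One of the eight endpoints kept, change in hemoglobin, is analysed for efficacy in a narrower population than the protocol and SAP Table 1 describe. Only the upward direction of the regression to the mean is claimed, not its size. The conclusion assumes that the reasons do not stand in documents not available here, such as the parent study SAPs or the SAP's front pages. It implies no motive. The sponsor should correct this, because the SAP as written gives no summary for protocol-specified endpoints and an efficacy estimate for a different population from the one named.

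**What to change.** 1. In SAP 7.3.3, summarise hemoglobin change under 7.1.2 in all women with a baseline value, and keep ≤ 10.5 g/dL as a labelled subgroup.
2. Restore the proportion reaching normal hemoglobin at Week 52, taken as ≥ 11.6 g/dL from the SAP's own lower limit. Note that this endpoint also selects on a low baseline.
3. Restore MIQ change to Week 52 for physical and for social and leisure activities, with descriptive statistics by parent study group and a rule for women without a recent period.
4. Restore the protocol's Kaplan-Meier time to response from randomization. Note that everyone in the Extension Study population completed 24 weeks, so parent-study dropouts are absent, and that Group C's curve combines placebo and active treatment.
5. For any protocol endpoint still left out, state the removal and the reason in SAP 1.1.

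The cost is about five tables (all-women hemoglobin change, normal hemoglobin, time to response, two MIQ items) plus SAP wording. No new data and no protocol amendment are needed.
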